Statistical Analysis Plan

Protocol Title: A randomized, double-blinded and placebo-controlled study on super-oxygenated water

Protocol Number: Inhale-001

ClinicalTrials.gov ID: NCT07016191

Principal Investigator:

[name].

[name]
[name]
[name]
United States

[contact]
[contact]

Sponsor:

Inhale, Inc

[name]
[name]
United States
[contact]

INTRODUCTION

The aim of this project is to test in a single-center randomized clinical trial, if ingestion of INHALE super-oxygenated water can augment blood oxygen saturation (SpO₂) and reduce heart rate (primary outcome measures) compared to their pre-ingestion levels as well as boost energy level and brain clarity (secondary outcome measures).

This statistical analysis plan (SAP) will give more detailed descriptions of the endpoints in the study and the corresponding analyses.

STUDY DESIGN

A total of 60 consenting subjects (research participants) will be recruited in the study. The study is a parallel-group clinical trial between two study arms to receive either INHALE super-oxygenated water (test article) or a source and taste-matched normal water (placebo control) randomized at 1:1 ratio with each arm enrolling 30 subjects. This is a double-blind study where neither the subject nor the investigator will know the assigned treatment. An unblinded research staff will perform the randomizations and dispense the blinded waters for use by blinded investigator.

The subjects will ingest 12 oz of water (about 10% of daily fluid intake which is similar to an average beverage size) in one administration. This amount is based upon available literature as a reasonable amount of fluid to drink and is aimed at not causing any dilution effect on blood oxygen saturation. The test article, INHALE water, contains dissolved oxygen at ~56 mg/L without any added sodium, sugar, protein or fat. The source and taste-matched normal water is packaged in the same way as the test article and contains dissolved oxygen at 0 mg/L without any added sodium, sugar, protein or fat. Only one dose (12 oz) of water will be ingested. Subjects will not be allowed to crossover from one arm to the other.

Pre-ingestion or baseline measurements of SpO₂ and heart rate will be measured. At one-minute post ingestion, SpO₂ and heart rate will be recorded. Subjects will complete clinical outcome assessments as patient reported outcome (PRO) for Energy level and Brain clarity assessment at pre- and post-ingestion time points.

Only one clinic visit will be necessary for a subject to complete the study. The overall study design is presented in Figure 1.

[figure not shown]

Fig 1: Study design schema

Sample Size Calculation

The primary outcome measure for the power calculation is the difference between INHALE super-oxygenated water and source and taste-matched placebo control water in the change of SpO₂ and heart rate. There are no prior studies known to the sponsor that measured similar effects following an oral ingestion to better advise sample size calculation. The sample size of 30 is selected to support analysis for an expected >1% increase in SpO₂ and an anticipated >1% decrease in heart rate as continuous measures in the experimental group with an alpha level of 0.05 powered at 80%.

AIMS AND OBJECTIVES

To demonstrate an improvement in blood oxygen saturation and reduction in heart rate following ingestion of super-oxygenated water. Additionally, the study will also measure whether the super-oxygenated water will enhance energy level and brain clarity.

OUTCOMES

Primary and secondary outcome measures will be assessed to answer the study aims and objectives. The analyses of the data are described below.

Primary Outcome Measures

1. Blood oxygen saturation (SpO₂). It will be measured at pre-ingestion and at one-minute post-ingestion of water by a pulse oximeter.
2. Heart rate. It will be measured at pre-ingestion and at one-minute post-ingestion of water by a pulse oximeter.

Secondary Outcome Measures

1. Energy level. It will be assessed at pre-ingestion and at one-minute post-ingestion of water through patient reported outcome measure (PRO) with a questionnaire (scale 1-10).
2. Brain clarity. It will be assessed at pre-ingestion and at one-minute post-ingestion of water through a PRO questionnaire (scale 1-10).

Safety Outcomes

Consumption of water is generally considered safe for human consumption. The sponsor is not aware of any health events related to drinking of super-oxygenated water. The production cycle of INHALE superoxygenated water encompasses a closed and aseptic cycle that ensures consistency and sterility of the product.

All adverse events will be collected, graded and reported.

STUDY POPULATION

Study Eligibility- Inclusionary Criteria

1. Legally adult (18 years or older) and either gender (male or female) will qualify
2. Subject must be willing to review and provide an informed consent for participation
3. Subject must agree to the study procedures including water ingestion, and SpO₂ and heart rate measurements

Study Eligibility- Exclusionary Criteria

1. Any active and life-threatening medical condition involving hepatic, renal, cardiac, respiratory, endocrinial, or gastrointestinal systems, or any blood disorder that may confound the study
2. Female subjects those are pregnant, nursing or planning to become pregnant
3. Subjects receiving any experimental medications or have undergone a major surgical procedure in last 30 days
4. Subjects previously utilized the test article (INHALE super-oxygenated water) within the last 24 hours, have undergone bariatric surgery or have received weight-loss medication
5. Subjects with known anemia, hemoglobinopathies or other comorbidities necessitating fluid restriction

Intent-to-treat (ITT)

All randomized study subjects will constitute ITT population. Collected data will be processed without any bias or selection and no subject data will be excluded from the analyses.

Per Protocol (PP)

All randomized study subjects completing the whole study period (completing all study assessments). The PP analyses will be performed in case of subjects not completing the entire study. Analyses of this population is seen as a sensitivity analysis to investigate whether the study conclusions are sensitive to assumptions regarding the pattern of missing data.

ANALYSES

The outcome measures will be presented using descriptive statistics; to summarize and describe the main features of the dataset using simple numbers (by the percent, mean, standard deviation and/or standard error) and graphs (scatter plot, histogram), helping to make large amounts of data understandable.

These analyses will provide a concise overview of characteristics like proportion of responders in a study group.

SpO2

The blood oxygen saturation will be measured twice (before and after water ingestion). The post-ingestion SpO2 will be compared with the pre-ingestion SpO2 from the same subject. An increased post-ingestion SpO2 over the pre-ingestion level will constitute treatment response and the SpO2 response rate (n/N) will be measured for both study arms. Pearson Chi-Square test will be applied to analyze categorical data (SpO2 response rate) between the arms for asymptotic significance (2-sided) at 5% level.

Heart Rate

The heart rate will be measured twice (before and after water ingestion). The post-ingestion heart rate will be compared with the pre-ingestion heart rate from the same subject. A reduction in post-ingestion heart rate over the pre-ingestion level will constitute treatment response and the heart rate response rate (n/N) will be measured for both study arms. Pearson Chi-Square test will be applied to analyze categorical data (heart rate response rate) between the arms for asymptotic significance (2-sided) at 5% level.

Energy Level

Energy level as reported by PRO assessment will be measured twice (before and after water ingestion). The post-ingestion energy level will be compared with the pre-ingestion energy level from the same subject. An increased post-ingestion energy level over the pre-ingestion level will constitute treatment response and the energy level response rate (n/N) will be measured for both study arms. Pearson Chi-Square test will be applied to analyze categorical

data (energy level response rate) between the arms for asymptotic significance (2-sided) at 5% level.

Brain Clarity

Brain clarity as reported by PRO assessment will be measured twice (before and after water ingestion). The post-ingestion brain clarity will be compared with the pre-ingestion brain clarity from the same subject. An increased post-ingestion brain clarity over the pre-ingestion level will constitute treatment response and the brain clarity response rate (n/N) will be measured for both study arms. Pearson Chi-Square test will be applied to analyze categorical data (energy level response rate) between the arms for asymptotic significance (2-sided) at 5% level.

MISSING DATA

As the study is designed to collect pairwise data at two time points, missing data (lost or uncollected data) at any time point will make the dataset unusable. When analyzing using the ITT population, simple imputation (last observation carried forward) will be used for both primary and secondary outcomes. A missing numerical data for a time point will be replaced with numerical data collected at the other time point for the same subject.

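### The stated aim is a before-after change with no placebo comparator while every test is between arms, and the 80% power is not stated for the responder test that is planned

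*SAP*

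**What the plan says.** **Aim and objective.** The SAP Introduction says the trial tests whether INHALE water "can augment blood oxygen saturation (SpO₂) and reduce heart rate (primary outcome measures) compared to their pre-ingestion levels". Aims and Objectives reads: "To demonstrate an improvement in blood oxygen saturation and reduction in heart rate following ingestion of super-oxygenated water". Neither sentence names placebo.

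**Sample Size Calculation.** The section opens on the between-arm contrast. Power is said to rest on the "difference between INHALE super-oxygenated water and source and taste-matched placebo control water in the change of SpO₂ and heart rate". Its last sentence then justifies 30 by an "expected >1% increase in SpO₂ and an anticipated >1% decrease in heart rate as continuous measures in the experimental group"; the error rate and power given there are 0.05 and 80%. It gives no SD of change, no assumed change on placebo and no response rates. The sponsor states that it knows of no prior studies to inform the calculation.

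**Analyses.** Each outcome is reduced to response or no response, where any improvement over the subject's own baseline counts. For SpO2: "Pearson Chi-Square test will be applied to analyze categorical data (SpO2 response rate) between the arms for asymptotic significance (2-sided) at 5% level". The same pattern holds for heart rate, energy level and brain clarity. Other summaries are descriptive. No within-arm significance test is specified.

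**The concern.** The aim, the power statement and the tests describe different comparisons. The aim is INHALE after against INHALE before. The tests are INHALE against placebo on the proportion of responders. The power statement names the between-arm difference in mean change in one sentence and a continuous change in the experimental group in another.

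Two things are at stake.

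- **What may be concluded.** A change one minute after drinking can include settling at rest, regression to the mean, the effect of drinking any water, and expectation. The placebo arm is there to remove these. The descriptive summaries and per-arm response rates will show within-arm change, and that change is what the aim literally asks about. Nothing in the SAP says that it is descriptive only.
- **What the 80% means.** Power for a continuous change, within one arm or between two, does not carry over to a chi-square on any-improvement responders with the same 30 per arm.

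**Working it through.** **Inputs from the SAP:** 30 per arm, 1:1; alpha 0.05; power 80%; two-sided tests (Analyses section); effect of more than 1%, continuous; response = any improvement over own baseline.

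**Assumptions, not in the SAP:** changes are normal with equal SD in the two arms; mean change on placebo is zero; no ties, so placebo response is 50%.

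**1. Can 30 per arm and 80% be reproduced?** No, because the SD of change is missing. Taking the effect as 1 unit of the measure, power by noncentral t at n = 30 is:

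| SD of change | Between arms (two-sample t) | Within one arm (paired t) |
|---|---|---|
| 1.0 | 97% | >99% |
| 1.5 | 72% | 94% |
| 2.0 | 48% | 75% |
| 3.0 | 25% | 42% |

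The 80% would be right between arms at SD 1.36 and within one arm at SD 1.89. The text does not settle which was meant.

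**2. Standardised effect d for 80% under each reading.**
- Between arms: noncentrality d√(30/2), 58 df. 80% needs d = 0.736 (0.736 × 3.873 = 2.85); 1/0.736 = 1.36.
- One group: noncentrality d√30, 29 df. 80% needs d = 0.529 (0.529 × 5.477 = 2.90); 1/0.529 = 1.89.
- The one-group d carried to two arms: 0.529 × 3.873 = 2.05, power 52%. Reaching 80% would then take 57 to 60 per arm.

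**3. Power of the planned chi-square at the same effects.** Under the assumptions, INHALE response is p₁ = Φ(d) and placebo response is p₀ = 0.5. Power = Φ[(p₁ − p₀ − 1.96·se₀)/se₁], with se₀ = √(2p̄(1 − p̄)/30) and se₁ = √((p₁(1 − p₁) + p₀(1 − p₀))/30).
- d = 0.736: p₁ = 0.769, p̄ = 0.6345, se₀ = 0.1243, se₁ = 0.1194. (0.269 − 0.2437)/0.1194 = 0.212, power 58%. About 50 per arm would be needed for 80%.
- d = 0.529: p₁ = 0.702, p̄ = 0.601, se₀ = 0.1265, se₁ = 0.1237. (0.2017 − 0.2478)/0.1237 = −0.373, power 35.5%, or about 36%. About 92 per arm would be needed.
- Check: summing the binomial probabilities of all 31 × 31 possible tables with chi-square above 3.84 gives 58.4% and 35.6%.

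**4. Sensitivity to whole-number readings.** If a 1-point mean gain at SD 1.36 is read in whole points, so that response needs a change above 0.5, the rates are Φ(0.5/1.36) = 64% against 36%. Power is then 61%, close to the 58% above.

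**5. A gain shared by both arms.** At SD 1.36 and a mean gain of 1 unit with INHALE, the between-arm t-test has 80% power if placebo gains 0, 29% if it gains 0.5, and 5% (type I error only) if it gains 1. The mean before-after gain with INHALE is the same in all three cases, and the stated aim does not tell them apart.

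**The case against.** The strongest reply is that the trial is plainly placebo-controlled. The title, the randomised parallel design, the opening sentence of the sample-size section and all four tests say so. Comparison with pre-ingestion levels can be read as defining the change variable, which is then compared between arms. The experimental-group phrase may only say where the benefit is expected. Much of this stands, and it limits the point in two ways.

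- A reader might infer that the SAP plans to claim efficacy from a before-after test in the INHALE arm. It does not. No such test is specified, and pre-to-post comparison serves only to classify each subject. The risk lies in the wording of the aim and in the lack of a rule on what meets it. A false-positive rate for a paired test would not be an error rate of this plan.
- A reader might infer that 30 was calculated for a one-group change, so that true power is 52%. The documents do not support this either. The section opens with the INHALE-placebo difference and gives no SD, so the one-group basis is only one reading.

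The reply does not remove the rest. The aim and objective still lack a comparator, the two power sentences still disagree, and on either reading the 80% refers to continuous measures while the test is on response rates.

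**Conclusion.** The point holds as an inconsistency in the SAP that should be corrected. The Introduction and Aims pose a before-after question, the tests pose a between-arm one, and nothing states which result meets the aim. The 80% can be neither confirmed nor refuted and does not describe the planned test.

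The size is conditional. If 30 per arm truly gives 80% for a between-arm t-test, the responder chi-square has about 58% power (77% against 50% responders). If 30 was set for a one-group change, it has about 36% (70% against 50%). These figures rest on normal changes, equal SDs, zero mean change on placebo and no ties. They illustrate the loss from continuous change to responder rate and do not estimate this trial's actual power.

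**What to change.** 1. Reword the Introduction and Aims so that the question is whether the response in SpO2 and heart rate from pre- to post-ingestion differs between INHALE water and placebo water.
2. State that efficacy conclusions rest only on the between-arm test and that within-arm changes are descriptive.
3. In the sample-size section, replace the reference to the experimental group with 'relative to placebo', so that the two sentences agree.
4. Restate power at 30 per arm for the between-arm test actually used as primary. If that stays the responder chi-square, give the assumed response rate in each arm. By the formula above, 30 per arm gives 80% power for INHALE response of about 41%, 54%, 65%, 75% or 83% against placebo response of 10%, 20%, 30%, 40% or 50%. If a continuous between-arm analysis is made primary instead, give the assumed SD of change and amend the Analyses section to match.

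Step 3 alone, or an SD added while the chi-square stays primary, would leave the planned test without a power statement.

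Cost: SAP wording only, with no change to data collection. The stated power may become less favourable.

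### The 80% power stated for a heart-rate fall of more than 1% cannot be reproduced, and at 1% it needs an SD of change of about 1 bpm or less

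*SAP*

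**What the plan says.** Under STUDY DESIGN, the trial is "randomized at 1:1 ratio with each arm enrolling 30 subjects". The Sample Size Calculation defines the powered quantity as the difference between INHALE water and "source and taste-matched placebo control water in the change of" SpO₂ and heart rate. It then ties the sample of 30 to a rise of more than 1% in SpO₂ and to "an anticipated >1% decrease in heart rate as continuous measures in the experimental group with an alpha level of 0.05 powered at 80" per cent. On where the assumptions come from, it says: "There are no prior studies known to the sponsor that measured similar effects following an oral ingestion".

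Heart rate is the second of two primary outcomes: "Heart rate. It will be measured at pre-ingestion and at one-minute post-ingestion of water by a pulse oximeter". In ANALYSES, any reduction counts as a response, and response rates are compared by Pearson chi-square for "asymptotic significance (2-sided) at 5% level".

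**The concern.** Power for a difference in means depends on the effect divided by the SD of the change. The SAP states a power but no SD, and it expresses the heart-rate effect as a percentage of a baseline that it does not give. One percent of a resting heart rate is less than one beat per minute for any baseline under 100 bpm. The SAP describes one pulse-oximeter value before ingestion and one after. For 80% power to hold at 1%, the change between two such values would have to vary very little from subject to subject, and the SAP offers nothing to show that it does.

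At stake is how a null result on a primary outcome is read. With the paragraph as it stands, a non-significant heart-rate result could be presented as evidence against a 1% fall from a trial with 80% power. The document does not establish that the trial has that power.

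**Working it through.** **Inputs from the SAP.** 30 per arm; alpha 0.05, taken as two-sided because the analysis section is two-sided; target power 80%; effect above 1%; between-arm difference in change. No loss allowance is stated and missing values are imputed, so n stays at 30 per arm.

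**Inputs not in the SAP, assumed here.** Baseline heart rate 60 to 90 bpm; SD of change 1 to 5 bpm.

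**Step 1: the stated figure.** It cannot be reproduced, because the SD and baseline are missing. What can be found is the SD that it requires.

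**Step 2: standardized difference for 80% power.** By normal approximation, (1.960 + 0.842) × √(2/30) = 0.723. With the noncentral t on 58 degrees of freedom it is 0.736, used below. A 1% effect therefore needs an SD of change of at most 1/0.736 = 1.36% of baseline.

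**Step 3: the same limit in bpm.** Between-arm limit = 1% of baseline / 0.736. If the sentence is read as a paired before-after test in the 30 INHALE subjects, the standardized difference for 80% is 0.529.

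| Assumed baseline (bpm) | 1% (bpm) | SD limit, between arms | SD limit, paired |
|---|---|---|---|
| 60 | 0.6 | 0.82 | 1.13 |
| 70 | 0.7 | 0.95 | 1.32 |
| 80 | 0.8 | 1.09 | 1.51 |
| 90 | 0.9 | 1.22 | 1.70 |

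**Step 4: power at exactly 1%, by assumed SD.** Noncentrality is δ / (SD × √(2/30)), with δ = 0.7 bpm at a 70 bpm baseline. Detectable difference is 0.736 × SD.

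| Assumed SD (bpm) | Power at 70 bpm | Detectable with 80% power | As % of 70 bpm |
|---|---|---|---|
| 1 | 76% | 0.7 bpm | 1.1% |
| 1.5 | 43% | 1.1 bpm | 1.6% |
| 2 | 27% | 1.5 bpm | 2.1% |
| 3 | 14% | 2.2 bpm | 3.2% |
| 5 | 8% | 3.7 bpm | 5.3% |

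For SDs of 2 to 5 bpm and baselines of 60 to 90 bpm, power runs from about 7% to 40%.

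**Step 5: other readings.**
- Paired, two-sided, 70 bpm: 46%, 24% and 12% at SDs of 2, 3 and 5 bpm. The highest value at an SD of 2 bpm or more is 66% (90 bpm, SD 2).
- One-sided between arms, 70 bpm: 38% at SD 2 and 13% at SD 5.
- Most generous combination (paired, one-sided, 90 bpm, SD 2): noncentrality 0.9 × √30 / 2 = 2.46 against a critical value of 1.70, giving about 78%.

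No reading reaches 80% for a 1% effect at an SD of 2 bpm or more.

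**Step 6: SpO₂, for contrast.** For 1 percentage point between arms, power is 97%, 80% and 48% at assumed SDs of 1.0, 1.36 and 2.0 points. The SAP gives no SD here either.

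**Step 7: the planned test.** Suppose changes are normal, placebo has no mean change, and the difference is 0.736 SD, so that the t-test has 80% power. The response rates (any fall) are then Φ(0.736) = 0.769 and 0.5. Their mean is 0.6345, so the null standard error is √(2 × 0.6345 × 0.3655 / 30) = 0.1243 and the alternative one is √((0.769 × 0.231 + 0.25) / 30) = 0.1194. Power is Φ((0.269 − 1.96 × 0.1243) / 0.1194) = Φ(0.21), about 58%.

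**The case against.** The strongest reply is that nothing here refutes the SAP. A reader might infer from the tables that the 80% is false and that the true power is 8 to 27%. The document does not support that: the range rests on a 70 bpm baseline and SDs of 2 to 5 bpm, none of which it states. At an SD of 1 bpm, power is 76% between arms and 96% paired.

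The stated effect is also a lower bound. At 70 bpm, a 3% fall with an SD of 2 bpm has 98% power, and a 5% fall with an SD of 3 bpm has 99%. For the same reason it does not follow that the SAP assumed one relative SD for both outcomes, since the two anticipated effects need not be equal. Nor does the SAP say that both primary outcomes must succeed, or how a null result will be interpreted.

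All of this stands, and it limits the point to an unsupported figure. It does not restore the figure. An effect given only as above 1% fixes no alternative at which power can be calculated. If the claim is meant for every effect above 1%, it has to hold close to 1%. The protocol, which is not at hand, might give an SD, but the SAP's remark about the absence of prior studies makes a sourced one doubtful.

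**Conclusion.** The point holds as a power figure without a stated basis for a primary outcome. That result needs no outside data beyond a plausible baseline: with 30 per arm, 80% power at a 1% difference requires an SD of change of about 1 bpm or less (0.82 to 1.22 bpm for baselines of 60 to 90 bpm; 1.13 to 1.70 bpm on the paired reading). The SAP gives no reason to expect so small an SD.

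The lower powers are conditional on the assumed SDs and should be quoted only with them. In particular, it would be too strong to say that the trial will almost always miss a 1% fall; even at an SD of 2 bpm and 70 bpm it would detect one about 27% of the time. The point is also separate from the planned use of response rates: moving to a t-test on change would leave the 80% just as unsupported, while keeping the chi-square lowers power further.

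**What to change.** Keep 60 subjects and revise the Sample Size Calculation as follows.

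- Remove the unqualified 80% for a 1% heart-rate decrease.
- State that 30 per arm, at two-sided 5%, gives 80% power for a between-arm difference of 0.74 SD of change.
- Give the detectable difference separately for each primary outcome, over an SD range labelled as assumed. For heart rate at SDs of 2 to 5 bpm it is 1.5 to 3.7 bpm, about 2 to 5% of 70 bpm. For SpO₂ it is 1 point at an SD of 1.36 points. If the sponsor has a source for the SD or baseline, cite it and use those values.
- Say that a non-significant heart-rate result does not exclude a 1% fall.
- Compute the pooled SD of change before unblinding and report it beside the assumed range.
- Tie the power to the test used. Either make the change score the primary heart-rate analysis, or keep the response-rate chi-square and state its power, which is about 58% where the t-test has 80% under the assumptions above.

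No extra subjects or measurements are needed. The cost is SAP wording, a less favourable stated power for heart rate, and a decision on the primary heart-rate test that must be made before unblinding.

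### All four between-arm tests are unadjusted chi-squares on any-change response, so collected baselines go unused, ceiling subjects dilute the contrast, and power is lost

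*SAP*

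**What the plan says.** The SAP's Study Design section sets 60 subjects, 30 per arm. SpO₂, heart rate, energy level and brain clarity are each recorded before ingestion and one minute after it.

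- **Sample Size Calculation.** The power target is the between-arm difference in change: more than 1% up for SpO₂ and more than 1% down for heart rate, "as continuous measures in the experimental group with an alpha level of 0.05 powered at 80" per cent. No SD is given.
- **Analyses, SpO2.** "An increased post-ingestion SpO2 over the pre-ingestion level will constitute treatment response". Then: "Pearson Chi-Square test will be applied to analyze categorical data (SpO2 response rate) between the arms for asymptotic significance (2-sided) at 5% level".
- **Analyses, Heart Rate.** "A reduction in post-ingestion heart rate over the pre-ingestion level will constitute treatment response", followed by "Pearson Chi-Square test will be applied to analyze categorical data (heart rate response rate) between the arms".
- **Analyses, Energy Level and Brain Clarity.** Any rise on the 1 to 10 scale is a response, with the same test.
- **Study Population, ITT.** "no subject data will be excluded from the analyses". No eligibility criterion limits the starting SpO₂ or score.

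Means and SDs appear only as descriptive statistics. The SAP has no continuous, stratified or covariate-adjusted comparison of the arms.

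**The concern.** The plan loses information in three separate ways.

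1. It keeps only the direction of change, so a one-point rise and a four-point rise count alike.
2. It does not adjust the between-arm comparison for baseline, although baseline is measured on everyone and predicts the post-ingestion value.
3. A subject at SpO₂ 100% or score 10 is a non-responder by definition but remains in N, which shrinks the difference in response rates. This third point does not apply to heart rate.

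The 80% power is also claimed for a continuous comparison that the SAP never makes, so it does not describe the planned tests. With 30 per arm, a real effect is more likely to be missed than the plan suggests.

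**Working it through.** **1. The plan's own figure.** Inputs from the SAP are 30 per arm, alpha 0.05, power 80% and an SpO₂ effect of 1% (read as 1 point). Two-sided testing is taken from the Analyses section. The formula is n = 2(1.960 + 0.842)² SD²/δ². Without an SD, 30 per arm cannot be reproduced, only solved backwards: SD of change = 1/(2.802 × √(2/30)) = 1.38, or 1.36 using the t distribution. Check: 2 × 7.85 × 1.38² = 29.9.

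**2. The planned test at that SD, with no ceiling.** Assume normal change with mean 0 on placebo. Response is then 50% on placebo and Φ(1/1.38) = 76.5% on the test article. Power = Φ{(0.265 − 1.96√(2 × 0.633 × 0.367/30))/√((0.250 + 0.180)/30)} = Φ{(0.265 − 0.244)/0.120} ≈ 57%. Reaching 80% would take 51 per arm.

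**3. ANCOVA on the same data.** Residual SD = 1.38 × √((1 + r)/2), where r is the pre-post correlation. For r = 0.3, 0.5, 0.7 and 0.8 the SD is 1.11, 1.20, 1.27 and 1.31, and power is 94, 90, 86 and 84%.

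**4. Ceiling dilution.** If a share c of each arm cannot respond, both rates are multiplied by (1 − c). Starting from step 2:

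| c | Response rates | Chi-square power | n per arm for 80% |
|---|---|---|---|
| 0 | 50.0 vs 76.5% | 57% | 51 |
| 10% | 45.0 vs 68.9% | 46% | 67 |
| 20% | 40.0 vs 61.2% | 37% | 86 |
| 30% | 35.0 vs 53.6% | 30% | 112 |

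This assumes ceiling subjects would otherwise have responded like everyone else. The simulation in step 5 relaxes that.

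**5. SpO₂ simulation.** Assumptions: whole-number readings capped at 100, between-subject SD 1, true shift 1 point, 30 per arm, 20,000 trials per cell, no continuity correction. Reading SD 0.96 is the anchor, since 0.96 × √2 = 1.36. Power (%) for chi-square / t-test on change / ANCOVA:

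| Mean baseline | SD 0.5 | SD 0.7 | SD 0.96 | SD 1.2 |
|---|---|---|---|---|
| 97 | 98/100/100 | 84/94/97 | 59/75/86 | 41/57/72 |
| 98 | 96/99/100 | 77/92/97 | 52/71/85 | 35/52/70 |
| 98.5 | 91/98/100 | 69/88/95 | 42/65/82 | 28/48/68 |

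- At mean 98, the share starting at 100 is 11, 14 and 17% for SD 0.7, 0.96 and 1.2.
- ANCOVA leads chi-square in all 12 cells, by 2 to about 40 points.
- At mean 98 and SD 0.96, not dichotomising is worth 71 − 52 = 19 points and baseline adjustment 85 − 71 = 14.
- Without the cap, chi-square power is 61% at SD 0.96 and 85% at SD 0.7, so the ceiling costs it 61 − 52 = 9 and 85 − 77 = 8 points.
- Keeping the binary endpoint but adjusting for baseline by logistic regression gives 62% (SD 0.96) and 85% (SD 0.7).
- With no true effect, rejection is 4.6–5.0% (chi-square), 4.7–5.2% (t-test) and 4.9–5.2% (ANCOVA).

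**6. Heart rate.** At an effect that gives the change t-test 80% power, chi-square has 59–60%. ANCOVA has 89, 85, 83 and 81% at correlations 0.5, 0.7, 0.8 and 0.9.

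**7. Energy level and brain clarity.** Assume mean 7.5, between-subject SD 1.7, shift 0.75 and a cap at 10. Power (%), in the same order as step 5, is 50/70/75 with reading SD 0.7 and 29/44/50 with reading SD 1.0.

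**The case against.** A response rate in all randomised subjects is a legitimate, pre-specified endpoint, and its type I error holds. This is therefore a question of efficiency, not validity. That stands and sets the severity.

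The strongest technical point is that direction of change resists outlying readings and linear ANCOVA does not. Let a share of SpO₂ readings fall low (mean 98, shift 1). Chi-square against ANCOVA is then:

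- 91 vs 82% at reading SD 0.5 with 5% of readings 4 points low;
- 84 vs 63% at SD 0.5 with 10% of readings 4 points low;
- 60 vs 60% at SD 0.7 with 10% of readings 4 points low;
- 68 vs 74% at SD 0.7 with 5% of readings 4 points low.

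At SD 0.96 with the same outliers, ANCOVA is again clearly ahead. The SAP does not rule out the reversal: in the first case the reading variance before capping is 0.25 + 0.05 × 0.95 × 16 = 1.01, so the change SD is √2.02 = 1.42, close to the back-solved 1.38. The gain is likely but not guaranteed.

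Three further points stand in part.

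- At the SAP's own 1% heart-rate effect, neither test is adequate. Assuming 70 bpm and correlation 0.8, chi-square against ANCOVA is 19 vs 28, 11 vs 16, 9 vs 11 and 8 vs 9% for change SD 2, 3, 4 and 5.
- ANCOVA does not undo the ceiling.
- Under the Missing Data section, a missing baseline would be replaced by the post-ingestion value, which would then enter the model as the covariate.

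**Conclusion.** The concern holds as something that should be changed. The textual facts are certain: four unadjusted any-change chi-squares, baselines used for no between-arm adjustment, ceiling subjects counted as failures, and a power claim made for a different, continuous comparison.

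The loss is of power and precision, with no bias towards a false positive. In the anchored SpO₂ scenario (mean 98, reading SD 0.96) it is about 33 points against ANCOVA: 19 from dichotomising and 14 from omitting baseline. The ceiling accounts for about 9 points of the chi-square's shortfall from its uncapped power.

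These sizes rest on an assumed SD, correlation, baseline mean and well-behaved reading error. The heart-rate gain is small at a 1% effect.

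**What to change.** - For each outcome, make the between-arm test an ANCOVA of the post-ingestion value on arm and the subject's own baseline. Test two-sided at 5% and report the adjusted mean difference with its 95% CI.
- Keep response rates as a supportive summary. If they are tested, use logistic regression on arm plus baseline.
- Tabulate by arm the number starting at SpO₂ 100% and at score 10, and keep every subject in the analysis, as the ITT paragraph requires.
- State as a limitation that linear ANCOVA does not remove the ceiling: at mean 98 and SD 0.96 it estimates 0.86 for a true 1.0.
- Add a rank-based version of the same model as a sensitivity analysis, to cover outlying readings.
- Add a sentence to Missing Data on how a missing baseline enters the model.

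**Cost.** Four test paragraphs are rewritten, with short additions, and no new data, visits or subjects are needed. The headline becomes an adjusted mean difference, which is less simple than a response rate. The change must be made before unblinding. The SAP does not give the trial's status; if unblinding has already happened, the new analysis should be labelled post hoc.
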